9.1 Definition and Assessment of Adverse Events

Adverse Event (AE) refers to any untoward medical event that occurs after a subject receives the investigational product, which may present as symptoms, signs, diseases, or abnormal laboratory tests, but is not necessarily causally related to the investigational product.

Serious Adverse Event (SAE) refers to an adverse medical event that occurs after a subject receives the investigational product, including death, life-threatening conditions, permanent or severe disability or functional loss, need for hospitalization or prolongation of hospitalization, and congenital anomalies or birth defects.

Adverse Drug Reaction (ADR) refers to any harmful or unintended reaction that may be related to the investigational product in clinical trials. There is at least a reasonable possibility of a causal relationship between the investigational product and the adverse event, i.e., the correlation cannot be excluded.

Suspected Unexpected Serious Adverse Reaction (SUSAR) refers to a suspected and unexpected serious adverse reaction whose nature and severity exceed the information in the investigator's brochure, labeling, or product characteristic summary of the investigational drug.

Investigators will closely observe adverse events in subjects. All adverse events reported by subjects or observed by investigators from randomization to the end of the study or early withdrawal must be recorded in medical records or CRFs, including laboratory and auxiliary examinations, and at least include the name of the AE, time of occurrence, end time,

severity, whether corrective treatment was given, outcome, and causal relationship with the study.

During the study, changes in vital signs, physical examinations, clinical manifestations, and laboratory tests of subjects should be evaluated. When signing the informed consent form, the name and phone number of the researcher whom the subject can contact in case of emergency, or when reporting any medical symptoms or subject-related AEs, must be provided. Pre-existing toxic reactions or AEs in subjects before participating in the clinical study are only recorded as AEs if the grade increases by one or more levels compared with the baseline assessment results during the study.

CTCAE Grade	Equivalent	Definition
Grade 1	Mild	Mild physical discomfort, not affecting daily life and function
Grade 2	Moderate	Physical discomfort, affecting daily life and function, no indication for treatment
Grade 3	Severe	Symptomatic, affecting daily life and function, with indication for treatment
Grade 4	Life-threatening/disability/functional loss	Life-threatening, with indication for emergency treatment, physical disability or intellectual impairment
Grade 5	Death	Adverse event resulting in death

AE and Study Correlation Analysis Table

	Definite	Probable	Possible	Suspected	Impossible
Reasonable time sequence with	+	+	+	+	-

medication/intervention					
Known drug/reaction type	+	+	+	+	-
Symptom relief or disappearance after stopping intervention	+	+	±	±	-
Recurrence of reaction after re-intervention	+	?	?	?	-
Cannot be explained by disease or concomitant medication	+	+	-	±	-

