4.4 Study Endpoints

Incidence of pulmonary complications within 3 days after surgery.

5. Study Subjects

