5.4 Exclusion Criteria

In Group A (FiO₂=30%), if SpO₂<94%, FiO₂ was increased; if FiO₂≥40%, the patient was excluded.

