5.6 Criteria for Terminating the Study

Considerations for the safety of subjects. For example, situations where it is inappropriate to continue the study, including: worsening of the condition, serious adverse events, poor compliance, etc. Postoperative occurrence of surgery-related complications such as postoperative bleeding requiring reoperation should result in termination of the study.

6. Research Methods and Technical Route

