6.7 Study-Related Imaging Examinations

Electrocardiogram

7. Efficacy Evaluation Criteria

Observation of primary outcome indicators: Time for dynamic lung compliance (Cdyn) to return to baseline after lung recruitment. Respiratory mechanics parameters and hemodynamic parameters at T1-T5 were recorded, including Cdyn, PIP, Ppeak, Pplat, Vt, PEEP, MP, Pdrive, BP, HR;

Observation of secondary outcome indicators: Degree of atelectasis immediately after extubation, evaluated by lung ultrasound; oxygenation index at T0-T5; incidence of hypoxemia and duration of oxygen therapy during PACU stay; pulmonary complications within 3 days after surgery, evaluated by postoperative chest X-ray or CT, with atelectasis assessed by lung ultrasound.

8. Observation Items and Detection Time Points

Before the first lung recruitment (RM1) after surgery starts (T1), immediately after RM1 (T2), before RM2 (T3), immediately after RM2 (T4), and immediately at the end of surgery (T5). Primary and secondary outcome indicators were observed. Degree of atelectasis immediately after extubation, evaluated by lung ultrasound; oxygenation index at T0-T5; incidence of hypoxemia and duration of oxygen therapy during PACU stay; pulmonary complications within 3 days after surgery, evaluated by postoperative chest X-ray or CT, with atelectasis assessed by lung ultrasound.

9. Observation of Adverse Events

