9.2.2 Handling of Adverse Events

9.2.3 Reporting of Adverse Events

Adverse events include intraoperative hypotension, bradycardia, hypoxemia, etc.

10. Quality Control and Quality Assurance

Investigators visited subjects one day before surgery to understand their medical history. Eligible subjects were enrolled only after obtaining their informed consent in strict accordance with the inclusion and exclusion criteria. If serious adverse events occurred during surgery, the trial should be stopped immediately.

11. Data Safety Monitoring

A data safety monitoring plan corresponding to the risk level will be formulated for the clinical study. All adverse events are recorded in detail, properly handled, and followed up until they are properly resolved or the condition is stable. Serious adverse events and unexpected events are reported to the ethics committee, competent authorities, sponsors, and drug regulatory authorities in a timely manner in accordance with regulations; the principal investigator regularly reviews all adverse events cumulatively, and if necessary, holds an investigator meeting to evaluate the risks and benefits of the study; emergency unblinding can be performed in double-blind trials to ensure the safety and rights of subjects; studies with greater than minimal risk will arrange independent data monitors to monitor study data, and high-risk studies will establish an independent data safety monitoring committee to monitor accumulated safety and efficacy data to make recommendations on whether to continue the study.

12. Statistical Analysis

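### Section 9.1 requires adverse-event recording only up to early withdrawal, so new events need not be recorded for a patient who leaves before day 3, when the search for pulmonary harm ends

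*Protocol*

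**What the plan says.** **Recording window.** Protocol section 9.1 requires that adverse events "from randomization to the end of the study or early withdrawal must be recorded in medical records or CRFs". It is the only place where adverse-event recording is given a start and an end.

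**Window for pulmonary harm.** Section 4.4 names as the study endpoint "Incidence of pulmonary complications within 3 days after surgery". Sections 7 and 8 list the same item as a secondary outcome: "pulmonary complications within 3 days after surgery, evaluated by postoperative chest X-ray or CT, with atelectasis assessed by lung ultrasound". They also list hypoxemia during the PACU stay.

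**Ways out of the study.**
- Section 5.4, Group A only: FiO2 is raised if SpO2 falls below 94%, and "if FiO₂≥40%, the patient was excluded".
- Section 5.6, any group: grounds for termination include "worsening of the condition, serious adverse events, poor compliance, etc". It adds: "Postoperative occurrence of surgery-related complications such as postoperative bleeding requiring reoperation should result in termination of the study".
- Section 10: "If serious adverse events occurred during surgery, the trial should be stopped immediately".
- Section 13: subjects may withdraw at any time.

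**Other safety text.** Section 9.2.1 asks for detailed recording of all adverse events and gives no time limits. Section 11 says: "All adverse events are recorded in detail, properly handled, and followed up until they are properly resolved or the condition is stable". The protocol summary lists no safety evaluation indicators.

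**The concern.** Several exits occur after the patient has been exposed to the assigned FiO2, and some are triggered by deterioration. These patients plausibly carry more risk of a later event than those who complete, yet for them the duty to record new events may end first. The background section itself calls high-concentration oxygen a risk factor for postoperative pulmonary complications, so the days after surgery are when harm of interest would be expected.

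The exit in 5.4 exists in one arm only. If it closes the recording window, Group A loses safety observation through a route that Groups B, C and D do not have, and a comparison of adverse events between arms would be distorted to that extent.

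Because the summary names no separate safety indicators, adverse-event recording is the main general source of safety data. An analysis plan cannot restore events that were never collected, so this has to be settled in the protocol.

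**Working it through.** The point rests on setting sections side by side. Arithmetic enters only for the number of patients who could be affected.

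**1. When does the duty end?** By 9.1, at the end of the study or at early withdrawal. For a patient who completes, the last assessment the protocol names is day 3 after surgery. For a patient who leaves during surgery or in the PACU, the gap between the end of the duty and that assessment is up to about 3 days.

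**2. Does the exit come after exposure?** Sections 4.2 and 6.3 set the group FiO2 after surgery starts and give the first recruitment 10 minutes later. The 5.4 exit depends on desaturation at the assigned FiO2, so it follows exposure. The section 10 exit is during surgery, and the reoperation ground in 5.6 is after it.

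**3. Does another section reopen the window?**
- Section 9.2.1 covers all adverse events but states no period, so it does not expressly extend the period in 9.1.
- Section 11 follows events until they resolve or stabilise. That concerns the outcome of an event already recorded. It does not expressly require a search for events that begin after withdrawal.
- Sections 7 and 8 collect PACU hypoxemia and 3-day pulmonary complications as outcomes. They do not say whether this continues after exclusion or withdrawal. Other kinds of event are not covered by them.

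No section expressly requires new events to be recorded after early withdrawal.

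**4. How many patients could be affected?** Inputs from section 12.2: 17 per group before inflation, 4 groups, 20% dropout.
- Per group: 17 / (1 − 0.20) = 21.25, rounded up to 22. This reproduces the plan's figure.
- Total: 4 × 22 = 88, also as stated.
- Allowance: 22 − 17 = 5 per group; 88 − 68 = 20 in total; 20 / 88 = 22.7%.

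The 20 is a ceiling within the plan's own allowance. It is reached only if every planned dropout is an early withdrawal after exposure, which the protocol does not say.

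**5. Can the loss of events be sized?** No. To see why, assume that a fraction 0.20 withdraws early, that withdrawn patients have RR times the risk of completers, and that all their events are missed. The shortfall in the reported rate then depends on a denominator that the protocol does not fix:

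| RR (assumed) | All patients as denominator: 0.2RR / (0.8 + 0.2RR) | Completers as denominator: 1 − 1 / (0.8 + 0.2RR) |
|---|---|---|
| 1 | 20% | 0% |
| 2 | 0.4 / 1.2 = 33% | 1 − 1/1.2 = 17% |
| 3 | 0.6 / 1.4 = 43% | 1 − 1/1.4 = 29% |

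The range from 0% to 43% comes entirely from assumptions. Missing every event in withdrawn patients is also an extreme case, since an event that causes the exit would normally be recorded before it. None of these values is an estimate for this trial.

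**The case against.** A reader might infer that withdrawn patients will have no new events recorded. The text does not support that. Section 9.1 says what must be recorded up to a point and forbids nothing afterwards, and 9.2.1 and section 11 speak of all adverse events without a stop at withdrawal. What stands is narrower: recording after withdrawal is not required.

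A reader might also infer that the pulmonary events of most interest are certain to be lost. They have a second route, because PACU hypoxemia and 3-day pulmonary complications are secondary outcomes with no stated stop at withdrawal. If outcomes are followed in every randomised patient, these events are captured whatever 9.1 says. The protocol does not commit to that follow-up, so the route is possible but not assured. It would in any case leave out events of other kinds, although those that 9.2.3 names (hypotension, bradycardia, hypoxemia) are introduced as intraoperative.

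Nor do 5.4 and 5.6 use the term of 9.1. They speak of exclusion and of termination of the study, and section 10 of stopping the trial. Exclusion could mean from the analysis only, in which case the 9.1 window stays open. This objection is sound, and the arm difference is therefore conditional on how these patients are classed. The undefined status is itself part of what the fix should settle.

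Finally, it may be tempting to quote a percentage by which event rates are understated. The 20% is a general allowance in the sample-size calculation, and the protocol gives neither event rates nor relative risks, so no such percentage can be supported.

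**Conclusion.** The point holds in limited form, as a data-collection rule that should be tightened. It is not a contradiction or a false statement. As written, 9.1 lets the duty to record new adverse events lapse at early withdrawal, and no other section expressly restores it to day 3.

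Two conditions govern how much this matters: that patients excluded under 5.4 or terminated under 5.6 or section 10 are treated as withdrawn in the sense of 9.1, and that their outcome assessment is not continued. If both apply, safety capture would be incomplete among patients whose exit may have followed from harm, and could differ by arm through the rule that exists in Group A only. At most 20 of 88 patients would be affected within the planned allowance. The number of events lost cannot be derived from the protocol.

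**What to change.** In section 9.1, replace the end of the recording period with wording such as: adverse events are recorded to day 3 after surgery for every randomised patient who received the assigned FiO2 or any recruitment, including patients excluded or withdrawn earlier, unless consent to data collection is withdrawn.

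State that events after exclusion or withdrawal are taken from the existing PACU and ward records. Reconcile the terms used in 5.4, 5.6, 9.1 and section 10, so that it is clear whether an excluded or terminated patient leaves treatment, analysis or observation. The change concerns data collection only and leaves the clinical rules in those sections as they are.

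The cost is one sentence and chart review for up to 3 days in about 20 inpatients at most, if dropout matches the plan. No new procedure is needed. Reported event counts may rise slightly.

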9.2 Recording and Handling of Adverse Events

9.2.1 Recording of Adverse Events

While observing efficacy, investigators should pay attention to adverse events or reactions. Investigators should explain to subjects and require them to truthfully report changes in their condition after medication, avoiding leading questions.

All adverse events, whether related to the trial drug or not, should be recorded in detail. Investigators should closely monitor clinical and laboratory evidence of adverse events in each patient, including the date of occurrence, symptoms, laboratory test results, severity, outcome, duration, and results of the event, and fill in the "Adverse Event Form". Investigators should promptly judge the causal relationship between the adverse event and the study drug and analyze the correlation between the adverse event and the trial drug. Concomitant medications should be recorded in detail, along with signatures and dates.

9.2.2 Handling of Adverse Events

9.2.3 Reporting of Adverse Events

Adverse events include intraoperative hypotension, bradycardia, hypoxemia, etc.

10. Quality Control and Quality Assurance

Investigators visited subjects one day before surgery to understand their medical history. Eligible subjects were enrolled only after obtaining their informed consent in strict accordance with the inclusion and exclusion criteria. If serious adverse events occurred during surgery, the trial should be stopped immediately.

11. Data Safety Monitoring

A data safety monitoring plan corresponding to the risk level will be formulated for the clinical study. All adverse events are recorded in detail, properly handled, and followed up until they are properly resolved or the condition is stable. Serious adverse events and unexpected events are reported to the ethics committee, competent authorities, sponsors, and drug regulatory authorities in a timely manner in accordance with regulations; the principal investigator regularly reviews all adverse events cumulatively, and if necessary, holds an investigator meeting to evaluate the risks and benefits of the study; emergency unblinding can be performed in double-blind trials to ensure the safety and rights of subjects; studies with greater than minimal risk will arrange independent data monitors to monitor study data, and high-risk studies will establish an independent data safety monitoring committee to monitor accumulated safety and efficacy data to make recommendations on whether to continue the study.

12. Statistical Analysis

12.1 Statistical Methods

All data were statistically analyzed using SPSS 26.0 software, with $P<0.05$ indicating a statistically significant difference. Count data were expressed as cases or percentages and analyzed using the Chi-square test or Fisher's exact test. Normality of measurement data was evaluated using the Kolmogorov-Smirnov test or Shapiro-Wilk test. Measurement data conforming to a normal distribution were expressed as mean \pm standard deviation ($x\pm s$) and analyzed using the t-test; count data with repeated measurements were analyzed using one-way ANOVA; skewed or unknown-distribution measurement data were expressed as median (interquartile range) [median (IQR)] and analyzed using the Mann-Whitney U test.

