6.1 Study Grouping

Grouping: Group A: FiO₂=30% (if SpO₂<94%, increase FiO₂; if FiO₂≥40%, the patient was excluded); Group B: FiO₂=40%; Group C: FiO₂=60%; Group D: FiO₂=80%. Inspired oxygen concentrations were adjusted to the respective group levels after the start of surgery.

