6.5 Study Flowchart

![img](Patients enter the operating room

Preoxygenation followed by tracheal intubation

Adjust to group-specific FiO₂ after surgery starts

Group A: FiO₂ 30%

Group B: FiO₂ 40%

Group C: FiO₂ 60%

Group D: FiO₂ 80%

First lung recruitment after 10 minutes

Record the duration of improved lung compliance

Next lung recruitment after compliance returns to baseline, and so on

All patients undergo lung recruitment immediately at the end of surgery,

Transfer to PACU, record incidence of hypoxemia and duration of oxygen therapy)

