12.2 Sample Size Calculation Process

88 cases
Sample size calculation process Based on preliminary experimental results, sample size was calculated using PASS, with a 20% dropout rate, resulting in a total sample size of 88 cases (22 cases in each group).

Input:

Power and Alpha

Power 0.95

Alpha 0.05

Group 4

Group Allocation Equal

Effect size

Means 30 34 50 53

K 1

σ 761519

Numeric Results
Means: 30 34 50 53

Power	Average	n	G	Total	K	Std Dev of Means	Standard Deviation	Effect Size	Alpha
0.9707	3.00	4		12	1.00	9.91	6.00	1.6515	0.0500
0.9875	4.00	4		16	1.00	9.91	7.00	1.4156	0.0500
0.9526	11.00	4		44	1.00	9.91	15.00	0.6606	0.0500
0.9526	17.00	4		68	1.00	9.91	19.00	0.5215	0.0500

One-Way Analysis of Variance F-Tests

Dropout-Inflated Sample Size (Continued)

Average Group Sample Size n	Group	Dropout Rate	Sample Size	Dropout-Inflated Enrollment Sample Size Ni	Expected Number of Dropouts Di
17.00	1 - 4	20%		17	22
	Total		68	88	5

13. Ethics of Clinical Research

The clinical study will follow the World Medical Association Declaration of Helsinki and other relevant regulations. Before the start of the study, the trial protocol will be implemented only after approval by the ethics committee. Before each subject is enrolled in the study, the investigator is responsible for fully and comprehensively introducing the purpose, procedures, and possible risks of the study to the subject or their agent, and a written informed consent form will be signed. Subjects should be informed that they have the right to withdraw from the study at any time. The informed consent form should be retained as a clinical study document for reference. The privacy and data confidentiality of subjects will be protected during the study.

14. Collection and Storage of Samples/Specimens

None.

15. Study Progress

Not available.

16. References

[2] Neira VM, Kovesi T, Guerra L, Campos M, Barrowman N, Splinter WM. The impact of pneumoperitoneum and Trendelenburg positioning on respiratory system mechanics during

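### The arms are ordered FiO2 levels, but no test named in Protocol 12.1 uses the order: a supportive trend analysis is worth adding beside a four-group test, which 12.1 must first assign to the primary outcome

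*Protocol*

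**What the plan says.** The groups form one quantitative factor at four rising levels. The flowchart in 6.5 starts with "Group A: FiO₂ 30" per cent, and 6.1 continues "Group B: FiO₂=40%; Group C: FiO₂=60%; Group D: FiO₂=80" per cent.

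Section 12.1 assigns tests by data type:
- Binary outcomes: "Count data were expressed as cases or percentages and analyzed using the Chi-square test" or Fisher's test.
- Normally distributed measurements: the t-test.
- Skewed measurements: the Mann-Whitney U test.
- One-way ANOVA appears only for repeated count data.

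The list in the protocol summary (section 1) is open-ended, but it names no trend test or dose contrast either.

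Section 12.2 sizes the trial differently. It uses "One-Way Analysis of Variance F-Tests" with "Group Allocation Equal", planning values "Means 30 34 50 53", and the largest of four SDs, 19. This gives 17 evaluable per arm, raised "with a 20% dropout rate, resulting in a total sample size of 88 cases (22 cases in each group").

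The primary objective (3.1) is the effect of different oxygen concentrations on the time for compliance to return to baseline. The end of section 2 adds that the best concentration is not known.

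**The concern.** When arms are doses of one factor, a test with one degree of freedom for movement along the dose scale concentrates its power on graded effects. A four-group F-test or chi-square test spreads the same information over three degrees of freedom. It would give the same p-value if the arm labels were shuffled. If the response rises or falls steadily with FiO2, that is a loss of power.

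The loss could matter most for PACU hypoxemia and pulmonary complications, for which the trial was not sized. An overall p-value also gives no estimate of how much the outcome changes per step of FiO2. A trend analysis is credible only if it is fixed before the data are seen, so the time to add it is now.

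**Working it through.** **Inputs from Protocol 12.2:** means 30, 34, 50, 53; SD 19; alpha 0.05; 17 evaluable and 22 enrolled per arm. **From 6.1:** doses 30, 40, 60, 80. **Assumptions:** the means are listed in dose order (the exact reverse gives the same power); the contrast is two-sided; all binary event rates.

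**1. Reproduce the protocol's figure.** The mean of the means is 41.75. The squared deviations are 138.06 + 60.06 + 68.06 + 126.56 = 392.75, so the SD of the means is √(392.75/4) = 9.91 and the effect size is 9.91/19 = 0.5215, as printed. The noncentrality is 17 × 392.75/19² = 18.50. With 3 and 64 df the power is 0.9526, as stated. Dropout: 17/0.8 = 21.25, rounded up to 22 per arm, 88 in total. The other three stated powers (0.9707, 0.9875, 0.9526) reproduce as well.

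**2. Linear dose contrast.** The mean dose is 52.5, so the centred doses c are −22.5, −12.5, 7.5, 27.5, with Σc² = 1475.
- Σc·mean = −675 − 425 + 375 + 1457.5 = 732.5.
- Linear sum of squares = 732.5²/1475 = 363.8, which is 363.8/392.75 = 92.6% of the between-arm variation.
- Noncentrality = 732.5 / (19 × √(1475/17)) = 4.14 on 64 df.
- Power = 0.983. Equally spaced scores give 0.982.

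**3. Primary outcome, SD 19**

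| Scenario | Overall F | Linear contrast |
|---|---|---|
| 17 per arm, planned effect | 0.953 | 0.983 |
| 22 per arm, planned effect | 0.988 | 0.996 |
| 17 per arm, 75% of effect | 0.75 | 0.86 |
| 17 per arm, 60% of effect | 0.54 | 0.69 |
| 17 per arm, 50% of effect | 0.39 | 0.53 |

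For 95% power at the planned effect the contrast needs 14 per arm (56 evaluable) against 17 (68 evaluable). If the four SDs 7, 6, 15, 19 are taken arm by arm, both tests exceed 99.9% at 17 per arm.

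**4. Binary outcomes.** Simulated power, Pearson chi-square (3 df) against Cochran-Armitage with dose scores. The rates are assumed because the protocol gives none.

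| Rates, A to D | Per arm | Chi-square | Trend |
|---|---|---|---|
| 10/15/25/35% | 17 | 0.33 | 0.50 |
| 10/15/25/35% | 22 | 0.42 | 0.61 |
| 5/10/20/30% | 17 | 0.40 | 0.59 |
| 5/10/20/30% | 22 | 0.49 | 0.70 |
| 5/10/15/20% | 22 | 0.19 | 0.35 |
| 2/4/6/10% | 22 | 0.11 to 0.12 | 0.20 |

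In the first four rows the trend test gains 17 to 21 points. In the last row both tests fail. With equal rates of 10% or 20% in all arms, the trend test with dose scores rejected in 4.6 to 5.1% of runs, so the gain is not bought with false positives.

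**5. When the response is not monotone.** With the planning means reordered to 30/50/53/34, the dose contrast has power of about 5% (11% with equal scores), while the F-test keeps 95.3%. With rates of 30/10/10/30% at 22 per arm, the trend test has 0.09 against 0.47 for the chi-square test.

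**The case against.** The strongest reply is that an unordered comparison of four arms is valid, and that a supplementary dose contrast is something a statistical analysis plan may add. That plan is not shown. This stands in part: if it already prespecifies a trend analysis, the trend half of this point is closed. But 12.1 does fix a test for each data type, and none of them uses the order.

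A second reply is that the protocol does not ask a trend question. It asks about differences between concentrations and notes that the optimum is uncertain. Its background gives reasons for and against high FiO2, so a non-monotone response is plausible. This stands, and step 5 of the working shows the cost of relying on a trend test alone. A trend test can therefore only support the overall test.

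Third, a reader might infer that the trial is underpowered for its primary outcome, or that its binary outcomes are known to be sparse. The documents support neither. At its own planning values the F-test already has 95% power, and the contrast adds 3 points, or under 1 point if all 22 per arm are evaluable. The larger gaps need a true effect below plan. No event rate appears anywhere, so both sparseness and the size of the binary gain are assumptions.

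Finally, there is a more basic fault in 12.1: the overall F-test exists only in the sizing and is never assigned to the primary outcome. For comparison, a t-test of the extreme pair (30 against 53, SD 19, 17 per arm) has power 0.928 unadjusted and 0.757 with Bonferroni over six pairs. A trend test alone would not repair that, so the fix starts there.

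**Conclusion.** The point holds as an inexpensive improvement, not as an error that invalidates the analysis. It is established that the arms are ordered, that no test named in 12.1 uses the order, and that the four-group test behind the sample size is not carried into 12.1 for the primary outcome.

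The size of the gain is conditional. For the primary outcome it requires a monotone effect, which the unlabelled planning means suggest but do not show, and it is material only if the true effect falls well short of plan. For the binary outcomes it requires both monotone rates and moderately high ones. It would be wrong to conclude that the unordered tests should be dropped: under a peaked or U-shaped response they are the ones that keep their power.

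**What to change.** In Protocol 12.1 (and in the statistical analysis plan, if there is one):

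1. Assign the four-group overall test used in 12.2 to the primary outcome, and state that it alone decides at the 0.05 level. This settles how alpha is used and reconciles 12.1 with 12.2.
2. Add one prespecified supportive trend analysis by FiO2 level. For measurement data, use a linear contrast with unequal-variance errors (the planning SDs run from 6 to 19) or the Jonckheere-Terpstra test. For PACU hypoxemia and pulmonary complications, use the Cochran-Armitage test, exact if events are few, alongside chi-square or Fisher.
3. Report the slope per 10 points of FiO2 with its 95% CI. In dose order, the planning means imply 10 × 732.5/1475 = 4.97 on the scale of the primary outcome.
4. State that the trend result does not replace the overall test.

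The cost is a few lines of wording and code, with no extra patients or measurements. The downside is that a trend test can miss a non-monotone response, which is why the overall test stays in place.
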